# **8 STUDY ADMINISTRATION**

## **8.1 Quality Assurance/Quality Control**

### **8.1.1 Direct Access to Source/Data Documents**

The Investigator will permit study-related monitoring, audits, IRB review, and regulatory inspections by providing direct access to source data and documents.

### **8.1.2 Periodic Monitoring**

The Sponsor or its designee will monitor all aspects of the study with respect to current Good Clinical Practice (GCP) and standard operating procedures for compliance with applicable regulations. These individuals must have access to all records necessary to ensure integrity of the data and will periodically review progress of the study with the Principal Investigator.

Monitoring of the study progress and conduct will be ongoing. The Sponsor or its designee will be responsible for the following:

- Monitoring study conduct to ensure that the rights of subjects are protected
- Monitoring study conduct to ensure study compliance with GCP guidelines
- Monitoring accuracy, completion, and verification of source documents for study data.

### **8.1.3 Audit and Inspection**

All data recorded during the study will be made available by the site for audit against source data and for compliance with GCP and specific protocol requirements.

#### **8.1.4 Confidentiality of Subject Data**

All information obtained during the conduct of the study that relates to an individual subject will be regarded as confidential. Throughout the study, participating subjects will be referenced using their allotted subject ID and initials. They will not be referred to by name in any document concerning the study or disclosed to any person not under the direct control of the Investigator.

### **8.2 Data Handling and Record Keeping**

#### **8.2.1 Electronic Case Report Forms (eCRFs)**

Adequate and accurate case records will be maintained and all relevant observations and data related to the study will be recorded. This will include (but will not be limited to) medical history/physical examination, vital signs, medication history, pregnancy tests, a check of inclusion and exclusion criteria, drug administration, a record of sample collection, AEs, and final evaluation.

The eCRFs will be signed electronically by the Principal Investigator after the review (date and time will be captured in the eCRF audit trail). After the completion of the study, completed eCRFs will be electronically transferred to the Sponsor and/or designee and stored in the archives according to the Data Management Plan for the study.

Completed eCRFs will be reviewed by the study monitor against the source documentation for accuracy and completeness. Once eCRFs are signed by the Investigator, the data manager will lock the eCRFs for data analysis.

#### **8.2.2 Study Records Retention**

All primary data that are a result of the original observations and activities of the study that are necessary for the reconstruction and evaluation of any study report will be retained in a secure archive at the study site for a period of at least 2 years after the last approval of a marketing application for a specified drug indication being investigated or, if an application is not approved, until at least 2 years after the investigation is discontinued and regulatory authorities are notified.

The Investigator must maintain adequate records for the study including completed CRFs, medical records, laboratory reports, signed ICFs, drug disposition records, adverse experience reports, information regarding subjects who discontinued, all correspondence with the IRB and the sponsor, and other pertinent data.

The Investigator will notify Arbor in writing of the relocation of any study records away from the clinical site after study closure. The Investigator must contact Arbor in writing prior to the destruction of any study records, or in the event of loss of any study records.

### **8.3 Termination of the Study**

The Sponsor reserves the right to terminate the study in the interest of subject welfare.

## **9 STATISTICAL ANALYSES**

### **9.1 Determination of Sample Size**

The primary efficacy endpoint is change from Baseline in AISRS total score at Visit 7 (Week 5). A Bonferroni adjustment will be utilized for the primary efficacy analysis where each AR19 dose will be tested against placebo separately using an alpha of 0.025 for each test.

Eighty-seven (87) subjects per treatment group will provide approximately 90% power to detect a 7.0-point difference in mean change from Baseline to Visit 7 in the AISRS total score between one of the AR19 doses and placebo with a standard deviation of 13.0 and Type I error of 0.025 using a two-sample test. To account for an approximate 20% dropout rate, a total of 104 subjects will be randomized to each of the three treatment groups for a total of 312 randomized subjects.

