## **3 INVESTIGATIONAL PLAN**

### **3.1 Description of Overall Study Design and Plan**

This randomized, fixed-dose, double-blind, multi-center trial investigates the safety and efficacy of AR19 in the treatment of ADHD in adults from 18 through 55 years of age.

Safety parameters and therapeutic effect will be evaluated throughout the trial.

Subjects will be randomized to 20 or 40 mg AR19 daily or placebo in a 1:1:1 ratio in this fixed dose study. The expected drop-out rate is projected at 20%.

The study will consist of:

- A 30-day Screening period and Baseline evaluation

- Titration with AR19 for 4 weeks to 20 or 40 mg daily dose or placebo
- At least two weeks at a stable dose of AR19 or placebo
- Post Withdrawal Follow Up phone call at Visit 8

Study visits will be conducted according to the Schedule of Assessments ([Table 6.1.1](#)).

Subjects who have signed an informed consent form (ICF) and who satisfy the inclusion/exclusion criteria will receive study drug twice daily, once in the morning and again four to six hours later. Study medication dosing will start at 10 mg/day and will be titrated in weekly intervals in 10-mg increments to 20 or 40 mg/day, depending on randomization.

It is anticipated that approximately 30 sites will participate in the study. Subject enrollment will continue until approximately 312 subjects are enrolled.

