#### **4.3 Removal of Subjects from Therapy or Assessment**

Any subject who withdraws from the study prior to completing the treatment period will be considered to have "prematurely discontinued" study participation. Subjects may withdraw or be withdrawn from the study for the following reasons:

- The subject wishes to discontinue study participation
- An adverse event or serious adverse event that imposes an unacceptable risk to the subject's health to continue in the study
- Major protocol deviations (e.g. failed to meet entry criteria, did not adhere to protocol requirements and/or impact integrity of subject level data)
- The subject is unable to tolerate 20 or 40 mg daily dose, depending on randomization
- Lost to follow up
- The subject becomes pregnant. If subjects are to withdraw due to pregnancy, the procedures in Section 7.6 should be followed
- The sponsor decides to terminate the study.

Although a subject is not obliged to give his/her reason for withdrawing prematurely, the Investigator will make a reasonable effort to obtain the reason while fully respecting the subject's rights. The procedures described for Early Termination (Section 6.1.5) will be performed, if possible. Every effort will be made to contact a subject who fails to attend a study visit, or does not respond by telephone, to ensure that the subject is in satisfactory health. The Medical Monitor will be informed of removal or early withdrawal of a subject from the study.

Withdrawn subjects will not be replaced.

If modifications in the experimental design, dosages, subject selection, etc. are indicated or required, such changes will be instituted only following consultation between the Sponsor and the Investigator and will be accomplished through formal amendments to this protocol and approval by the appropriate review committees.

This study may be discontinued at any time if, in the opinion of the Principal Investigator or the Sponsor, continuation of the study represents a significant medical risk to participating subjects.

Arbor retains the right to terminate the study at an individual study site or at all study sites for administrative reasons such as, but not limited to: unacceptable subject accrual, failure of the Principal Investigator to conduct the study according to protocol, or failure to complete study case report forms (CRFs) or maintain study records satisfactorily.

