### **9.2 General Methodology**

All continuous study assessments will be summarized by treatment and time point using descriptive statistics (n, mean, median, standard deviation, minimum, and maximum). All categorical study assessments will be summarized by treatment and time point using frequency counts and percentages. Hypothesis testing, unless otherwise indicated, will be two-sided and performed at the 5% significance level.

A detailed statistical analysis plan (SAP) will be written and finalized prior to database unblinding.

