#### **9.3.2 Full Analysis Set (FAS) Population**

All patients who are randomized, receive at least one dose of study medication, and had one or more post-Baseline on-treatment primary efficacy assessment(s) will be included in the FAS Population. The FAS Population is the primary analysis population for clinical efficacy. Results will be presented "as randomized."

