## **9.4 Primary Efficacy Analysis**

The primary efficacy analysis will be performed on the FAS population.

For the primary efficacy endpoint, change from baseline in AISRS at Visit 7 (Week 5), the two AR19 dose levels (20 and 40 mg/day) will be compared with placebo. To account for these comparisons, a Bonferroni multiple comparison adjustment will be utilized. Both comparisons will be conducted at the 0.025 (0.05/2) alpha level. No other adjustments for multiplicity will be applied to any other endpoints or comparisons.

Change from Baseline in AISRS at Visit 7 will be compared between each of the two different AR19 dose groups and the placebo group using a restricted maximum likelihood (REML)-based mixed model for repeated measures (MMRM). This model will include fixed effects for treatment, week, baseline AISRS, and the treatment-by-week interaction. Study week will be included in the model as a categorical variable. Within this model, pairwise comparisons (using least squares [LS] mean contrasts) will be made to compare AISRS at Visit 7 for each AR19 dose level with placebo separately (primary efficacy outcome). Treatments will also be compared at other weeks as secondary analyses. If differences between baseline characteristics exist between the three treatment groups in this comparison, it will be investigated whether adjustment for these characteristics is clinically relevant and necessary as a sensitivity analysis.

All available data will be used; there will be no imputation of missing data.

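### The dropout allowance is short: 104 per arm leaves about 83 at the projected 20% dropout, not the 87 behind the power statement; keeping 87 would take 109 per arm

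*Protocol*

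**What the plan says.** Protocol 9.1 gives the basis: "Eighty-seven (87) subjects per treatment group will provide approximately 90% power" to detect a 7.0-point difference in AISRS change at Visit 7, with a standard deviation of 13.0. On multiplicity, "each AR19 dose will be tested against placebo separately using an alpha of 0.025 for each test". Protocol 9.2 sets the sidedness: "Hypothesis testing, unless otherwise indicated, will be two-sided". The Synopsis names the test as a two-sample t test.

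The dropout step follows in Protocol 9.1: "To account for an approximate 20% dropout rate, a total of 104 subjects will be randomized to each of the three treatment groups", giving 312 in total. The Synopsis and SAP 2.7 repeat the same 87, 20%, 104 and 312. None of the three shows how 104 was obtained.

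Three other places bear on the point:

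- Protocol 3.1 and SAP 2.3 give the dropout rate without a qualifier: "The expected drop-out rate is projected at 20" per cent.
- Protocol 4.3: "Withdrawn subjects will not be replaced".
- Protocol 9.3.2 and 9.4 define who and what enters the primary analysis. Subjects who "had one or more post-Baseline on-treatment primary efficacy assessment(s) will be included in the FAS Population", and "All available data will be used; there will be no imputation of missing data".

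**The concern.** A dropout rate is a share of those randomized. To finish with n subjects when a proportion d is lost, one randomizes n / (1 − d). The figure of 104 looks instead like 87 increased by 20%, since 87 × 1.2 = 104.4. That adds 20% of the smaller number and falls short of replacing 20% of the larger one. Because no formula is given, this can only be said to fit the stated figure.

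At stake is whether the sample-size paragraph means what it appears to mean: that the trial keeps about 90% power, by its own calculation, at its own projected dropout. A reader will take 104 as the number that protects 87. With no replacement of withdrawals, nothing else in the plan makes up the difference.

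**Working it through.** **Inputs.** Difference 7.0, SD 13.0, 87 per arm, about 90% power, alpha 0.025 per dose, 20% dropout, 104 per arm and 312 in total (Protocol 9.1); two-sided testing (Protocol 9.2); two-sample t test (Synopsis); 1:1:1 allocation (Protocol 5.4); no replacement (Protocol 4.3).

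**1. Reproduce the 87.** For n per arm, power comes from the noncentral t distribution with 2n − 2 degrees of freedom and noncentrality 7 / (13 × √(2/n)), at two-sided alpha 0.025.

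| n per arm | Noncentral t | Normal approximation |
|---|---|---|
| 87 | 90.0% | 90.5% |
| 86 | 89.7% | 90.1% |
| 83 | 88.5% | 89.0% |

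So 87 is the smallest n that reaches 90% by the named test. A one-sided alpha of 0.025 would need only 73 (normal approximation), which confirms that the sizing is two-sided. This part of the plan is sound.

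**2. Check the dropout step.**

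- Remaining from 104 at 20% dropout: 104 × 0.8 = 83.2, about 83 per arm, which is 4 below 87.
- Needed to keep 87: 87 / 0.8 = 108.75, so 109 (109 × 0.8 = 87.2, whereas 108 × 0.8 = 86.4).
- Total needed: 3 × 109 = 327. Shortfall: 109 − 104 = 5 per arm and 327 − 312 = 15 overall.
- Dropout that 104 can absorb: 1 − 87/104 = 17/104 = 16.3%.

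**3. Power consequence by the plan's own method.** With 83 completers per arm, t-test power per dose is 88.5% against 90.0% at 87, a loss of about 1.5 percentage points. The normal approximation gives the same loss (90.5% to 89.0%).

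**4. How far the primary model might change this.** The MMRM's power depends on the correlations between visits and on when subjects drop out, and the documents give neither. As an assumption, take baseline adjustment alone, with correlation r between baseline and change, so that the SD becomes 13 × √(1 − r²):

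| r (assumed) | 83 per arm | 87 per arm |
|---|---|---|
| 0.1 | 88.8% | 90.4% |
| 0.2 | 89.8% | 91.3% |
| 0.3 | 91.4% | 92.7% |

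The gap between 83 and 87 stays at 1.3 to 1.5 points over this range. The table leaves out whatever is gained from the partial data of subjects who drop out.

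**The case against.** The strongest reply accepts the arithmetic and says that it hardly matters.

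- **The plan speaks only of approximate power, and 88.5% is arguably still about 90%.** The loss is also small beside the uncertainty in the inputs: at 83 per arm, 90% returns if the SD is 12.7 instead of 13.0, or the difference 7.16 instead of 7.0. This stands as a comment on size. It does not make 104 the number that retains 87 at 20% dropout.
- **The word approximate also qualifies the dropout rate.** The figure 104 corresponds to 16.3%, and Protocol 3.1 and SAP 2.3 state 20% without qualification. This does not stand.
- **83 is a count of completers, not the number in the primary analysis.** AISRS is rated at five post-baseline visits and at early termination, the FAS asks for only one on-treatment assessment after baseline, and the model adjusts for baseline. With r of about 0.22, baseline adjustment alone would bring 83 per arm back to 90%. This stands: 88.5% must be labelled completers-only and must not be presented as the power of the MMRM. But the plan chose to size the trial by a two-sample test and to add a dropout allowance, and neither document claims that the model makes up a shortfall.
- **Two doses are tested.** If both had the 7-point effect, the chance that at least one succeeds would be about 96% at 83 per arm and 97% at 87 (normal approximation, correlation 0.5 between the two tests). This is fair, but the plan's power statement is per dose, and that is the statement at issue.

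**Conclusion.** The concern holds. The 87 per arm is right; the claim that 104 per arm allows for about 20% dropout is wrong by 5 subjects per arm, and the error stands in all three statements of the sample size. It is certain as arithmetic, given the ordinary reading that the allowance is meant to leave 87 subjects. Its effect is small: about 1.5 points of power per dose by the two-sample t test on completers, and possibly nothing in the planned MMRM. It introduces no bias and leaves type I error alone. The trial is not seriously underpowered, but the plan's sample-size justification should be corrected because readers will rely on it.

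**What to change.** Keep 104 per arm and 312 in total, and correct the statement in the Synopsis, Protocol 9.1 and SAP 2.7. Suggested wording:

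> Randomizing 104 subjects per arm retains 87 (approximately 90% power per dose) with up to about 16% dropout. At the projected 20% dropout, about 83 per arm would complete, and power per dose by the two-sample t test on completers is about 88.5%. The primary MMRM uses all available data and adjusts for baseline, so this calculation does not give its power.

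If the sponsor prefers to protect 87 completers at 20% dropout, the figures become 109 per arm and 327 in total, which is 15 more subjects.

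The wording change leaves enrolment, design, alpha and analysis as they are. Two of the three places are in the protocol, where Protocol 10.1 sends every amendment to the IRB, so the correction could reasonably travel with the next amendment.

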### **9.2 General Methodology**

All continuous study assessments will be summarized by treatment and time point using descriptive statistics (n, mean, median, standard deviation, minimum, and maximum). All categorical study assessments will be summarized by treatment and time point using frequency counts and percentages. Hypothesis testing, unless otherwise indicated, will be two-sided and performed at the 5% significance level.

A detailed statistical analysis plan (SAP) will be written and finalized prior to database unblinding.

### **9.3 Subject Populations for Statistical Analysis**

The three analysis populations for this study are defined below. Identification of the subjects to be included in each analysis population will be determined prior to database unblinding.

#### **9.3.1 Safety Population**

All patients who are randomized and receive at least one dose of study medication will be included in the Safety Population. The Safety Population is the primary analysis population for safety assessments. Results will be presented "as treated."

#### **9.3.2 Full Analysis Set (FAS) Population**

All patients who are randomized, receive at least one dose of study medication, and had one or more post-Baseline on-treatment primary efficacy assessment(s) will be included in the FAS Population. The FAS Population is the primary analysis population for clinical efficacy. Results will be presented "as randomized."

### **9.3.3 Per Protocol Population**

All patients who are in the FAS population and who do not have any major protocol deviations will be included in the PP Population. The PP Population will be used as a sensitivity analysis for clinical efficacy.

## **9.4 Primary Efficacy Analysis**

The primary efficacy analysis will be performed on the FAS population.

For the primary efficacy endpoint, change from baseline in AISRS at Visit 7 (Week 5), the two AR19 dose levels (20 and 40 mg/day) will be compared with placebo. To account for these comparisons, a Bonferroni multiple comparison adjustment will be utilized. Both comparisons will be conducted at the 0.025 (0.05/2) alpha level. No other adjustments for multiplicity will be applied to any other endpoints or comparisons.

Change from Baseline in AISRS at Visit 7 will be compared between each of the two different AR19 dose groups and the placebo group using a restricted maximum likelihood (REML)-based mixed model for repeated measures (MMRM). This model will include fixed effects for treatment, week, baseline AISRS, and the treatment-by-week interaction. Study week will be included in the model as a categorical variable. Within this model, pairwise comparisons (using least squares [LS] mean contrasts) will be made to compare AISRS at Visit 7 for each AR19 dose level with placebo separately (primary efficacy outcome). Treatments will also be compared at other weeks as secondary analyses. If differences between baseline characteristics exist between the three treatment groups in this comparison, it will be investigated whether adjustment for these characteristics is clinically relevant and necessary as a sensitivity analysis.

All available data will be used; there will be no imputation of missing data.

## **9.5 Secondary Efficacy Analyses**

The primary analysis will be repeated on the PP population using the MMRM analysis described in Section [9.4](#).

The secondary efficacy outcomes include:

- AISRS hyperactivity/impulsivity subscale scores
- CGI-S
- CGI-I
- BRIEF-A

For the AISRS, the proportion of responders (defined as a subject who has a change from Baseline of 30% or greater in the AISRS) will also be presented.

The number and percentage of subjects who have each category of the CGI-S and CGI-I at each time point will be presented by treatment group. Cochran-Mantel-Haenszel row mean score tests will be used to compare the treatment groups. CGI-S and CGI-I results will also be summarized treating the responses as continuous values. A MMRM will be utilized to

compare treatments at each time point. The model will include fixed effects for treatment, week, and the treatment-by-week interaction.

BRIEF-A will be summarized descriptively over time utilizing observed and change from Baseline scores. Treatments will be compared at each time point utilizing MMRM models on change from Baseline scores. The model will include fixed effects for treatment, week, baseline value, and the treatment-by-week interaction.

## **9.6 Exploratory Endpoints**

Similar to the BRIEF-A, DERS and ASQ scale scores will be summarized descriptively over time utilizing observed and change from Baseline scores. Treatments will be compared at each time point utilizing MMRM models on change from Baseline scores. The model will include fixed effects for treatment, week, baseline value, and the treatment-by-week interaction.

The pharmacokinetic analysis and reporting will be covered in a separate SAP and report.

## **9.7 Handling of Drop-Outs or Missing Data**

For subjects who discontinue prematurely, a MMRM approach will be used to address missing data. Other imputation methods (e.g., last observation carried forward [LOCF] or multiple imputation) may be used as sensitivity analyses. Full details will be described in the SAP.

## **9.8 Safety Analyses**

All safety data will be analyzed descriptively by treatment group using the Safety Population.

